## 9.4.2. Secondary Efficacy Endpoints

The secondary endpoints will be assessed hierarchically in the following order:

- The CGI change between the baseline and the end of maintenance dose
- TMC-response defined as improvement ≥ 2 in TMC score between the baseline and the end of maintenance dose in each group
- The percentage of change in TMC score
- The PGI change between the baseline and the end of maintenance dose
- Total Motor Score (TMS) of the UHDRS®
- Gait sub-score of the UHDRS®
- Dystonia sub-score of the UHDRS®
- EQ-5D-5L measuring quality of life

Secondary efficacy endpoints will be analyzed using the mITT Population.

For continuous efficacy endpoints with longitudinal data, the same MMRM model, as described for the primary endpoint will be performed. For other continuous efficacy endpoint measured at baseline and end of maintenance dose, an ANCOVA model will be used.

Categorical efficacy endpoints will be analyzed using a logistic regression model.

The type I error will be set at 0.05 (two-sided) and the coverage level of confidence intervals to 95% for all secondary efficacy analyses. No multiplicity adjustment will be applied for the statistical inferences of the secondary efficacy endpoints.

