#### 4.1 Conventions

#### 4.1.1 Baseline definition

Baseline is defined according to the endpoint as follows:

- For the Total Maximal Chorea score (TMC), and motor part of Unified Huntington's Disease Rating Scale (UHDRS-TMS) the baseline is defined as the average of the values for Visit 0 and Visit 1.
- The severity of choreic symptoms is assessed at Visit 1 with Clinical Global Impression-severity (CGI-S) scale and Patient Global Impression-severity (PGI-S) scales. Score of these 2 scales is assessed at baseline but cannot be used as baseline value when calculating changes to baseline, since change is already assessed at each visit (Visit 2 to Visit 6) with Clinical Global Impression of Change (CGI-C) and Patient Global Impression of Change (PGI-C).
- For EQ-5D, Barnes Akathisia Rating Scale (BARS), Montreal Cognitive Assessment (MoCA) scale and Problem Behavior Assessment short form (PBA-s) baseline is the value at Visit 1.

Statistical Analysis Plan	Version 1.0		Page 13 of 37
Sponsor	SOM Biotech	Protocol No	SOMCT03

- For the Total Functional Capacity score (TFC), Columbia Suicide Severity Rating Scale (C-SSRS), Beck Depression Inventory (BDI), Epworth Sleepiness Scale (ESS), ECG and vital signs, baseline is defined as the value at Visit 1.
- For Functional Assessment (FA) of the UHDRS baseline is at Visit 0.
- For laboratory data (haematology and clinical chemistry), baseline is at Visit 0.
- For any other parameter, baseline is defined as the last available measurement before the first administration of study drug, i.e., the value of the parameter at Visit 0 or at Visit 1.

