## 4.7.2.1 Clinical Global Impression

The CGI-Severity (CGI-S) assessed at baseline is a 7-point Likert Scale that asks the clinicians to rate, considering their total experience with this type of patients, the level of illness due to chorea on the illness severity ranging from normal (1) to extremely ill (7) (CGI-Severity).

Statistical Analysis Plan	Version 1.0		Page 21 of 37
Sponsor	SOM Biotech	Protocol No	SOMCT03

Then, after therapy initiation, the CGI-Change (CGI-C) asks the clinician to assess the overall global change in the choreic symptoms since the start of study drug dosing, in a 7-point Likert Scale ranging from very much worse (7) to very much improved (1).

CGI-S will be assessed at the inclusion (Visit 1 at Day 0), and CGI-C at each following visit (from V2 to V6). For the CGI-C, patients with a score of 1 (very much improved), 2 (much improved) or 3 (minimally improved) will be defined as "Improved" and patients with a score of 4 (No change), 5 (Minimally worse), 6 (Much worse) and 7 (Very much worse) will be defined as "Not improved".

CGI-S (baseline characteristic) and CGI-C results will be analysed descriptively at each visit.

A logistic regression model will be performed for CGI-C at V5 (end of maintenance dose) including the treatment group as the main factor in the model. Estimates along with 95% confidence intervals for the difference in response proportion and the odds ratio of response will be derived from this model.

In addition, histogram will be presented.

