## 4.7.2.2 Percentage of responders on TMC score

TMC score is assessed at each visit from V0 to V6.

V0 and V1 values are used to calculate the baseline (mean of the 2 values), and V4 V5 values for the end of maintenance dose.

Assessment at V6 occurs after the drug interruption with one week at 200 mg OD and the last week under placebo.

TMC score evolution will be assessed at each visit.

The number and percentage of responders with an improvement of at least 2 points in the TMC score will be calculated in each treatment group at each visit.

The TMC response status ("Responder" vs. "Not responder") will be described at each visit.

Logistic regression model will be performed for responders on TMC score at V5 (end of maintenance dose) including the treatment group as the main factor in the model. Estimates along with 95% confidence intervals for the difference in response proportion and the odds ratio of response will be derived from this model.

In addition, histogram will be presented.

This analysis will be repeated on the PP population.

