## 4.7.2.4 Patient Global Impression

The PGI-Severity (PGI-S) is a 7-point Likert Scale that asks the patients to assess the severity of their choreic symptoms at baseline ranging from not present (1) to extremely severe (7).

Then, after therapy initiation, the PGI-Change (PGI-C), asks the patients to assess the overall global change in their choreic symptoms and their quality of life since the start of study drug dosing, in a 7-point Likert Scale ranging from very much worse (7) to very much improved (1).

PGI-S will be assessed at the inclusion (Visit 1 at Day 0), and PGI-C at each following visit (from V2 to V6). For the PGI-C, patients with a score of 1 (very much improved), 2 (much improved) or 3 (minimally improved) will be defined as "Improved" and patients with a score of 4 (No change), 5 (Minimally worse), 6 (Much worse) and 7 (Very much worse) will be defined as "Not improved".

PGI-S and PGI-C results will be analysed descriptively at baseline and post-baseline visit respectively.

Logistic regression models will be performed for PGI-C at V5 (end of maintenance dose) including the treatment group as the main factor in the model. Estimates along with 95% confidence intervals for the difference in response proportion and the odds ratio of response will be derived from this model. In addition, histogram will be presented.

This analysis will be repeated on the PP population.

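### The logistic models for TMC response, CGI-C and PGI-C name no baseline covariate; pre-specifying one already collected is a cheap precision gain, not a validity repair

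*SAP*

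**What the plan says.** Three binary efficacy analyses are described in almost the same words.

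- TMC response (SAP 4.7.2.2): "Logistic regression model will be performed for responders on TMC score at V5 (end of maintenance dose) including the treatment group" as main factor.
- CGI-C, the key secondary endpoint (SAP 4.7.2.1): "A logistic regression model will be performed for CGI-C at V5 (end of maintenance dose) including the treatment group as the main factor".
- PGI-C (SAP 4.7.2.4): "Logistic regression models will be performed for PGI-C at V5 (end of maintenance dose) including the treatment group as the main factor".

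Each section asks for both a difference in response proportions and an odds ratio, with 95% confidence intervals, from the fitted model. None lists a covariate. Protocol 9.4.2 adds no model terms: "Categorical efficacy endpoints will be analyzed using a logistic regression model".

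The continuous efficacy models do name a covariate, always the baseline of the outcome analysed:

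- baseline TMC in the primary MMRM and in the observed-case ANCOVA (SAP 4.7.1), and, by reference to the primary model, in the percentage-change MMRM (4.7.2.3);
- baseline TMS, gait or dystonia score (4.7.2.5);
- baseline EQ-5D score (4.7.2.6).

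On the global scales, SAP 4.1.1 says: "The severity of choreic symptoms is assessed at Visit 1 with Clinical Global Impression-severity (CGI-S) scale", and it treats PGI-S in the same way. It then rules these two scores out as the starting value for a change score, because CGI-C and PGI-C already rate change. It is silent on using them as covariates, and no model in either document contains them.

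**The concern.** TMC response is an absolute fall of at least 2 points, in patients who enter at 10 or more on a 28-point scale. Baseline is also one of the two terms in the change itself, so some correlation between baseline and change is to be expected. The sponsor treats baseline TMC as relevant elsewhere: it is the primary model's covariate and defines a planned subgroup (SAP 3.6). Protocol 5.6 describes randomisation as site-specific and mentions no stratification on TMC.

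If baseline predicts response, a model without it leaves explainable variation in the comparison. The primary result is baseline-adjusted and the responder result is not, so the two may differ partly for that reason. The key secondary also belongs to the family-wise testing strategy (SAP 2.2 and 4.7.2), so its model terms should be settled in advance. What is at stake is precision and pre-specification.

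**Working it through.** **1. The plan's own figure.** Inputs from SAP 1.4: difference 2.5, SD 3.5, two-sided alpha 0.025, two-sample t-test. The exact noncentral t gives power of 79.4% at 38 per arm and 80.5% at 39, so the stated 39 reproduces. This sizing concerns the primary endpoint and does not depend on the binary models. The documents give no power for any binary endpoint.

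**2. Response rates implied for TMC response.** Take change as normal with SD 3.5 and response as change <= -2. The placebo mean change m is not in the documents and is assumed.

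- Placebo rate = Phi((-2 - m)/3.5); active rate = Phi((-2 - m + 2.5)/3.5).
- m = 0: Phi(-0.571) = 28.4% and Phi(0.143) = 55.7%.
- m = -1: Phi(-0.286) = 38.8% and Phi(0.429) = 66.6%.

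**3. Treatment-only power by formula**, 39 per arm, two-sided 0.05 (SAP 4.7.2). For m = 0:

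- Difference = 0.273.
- SE under the null = sqrt(2 x 0.4203 x 0.5797/39) = 0.1118.
- SE under the alternative = sqrt((0.2839 x 0.7161 + 0.5568 x 0.4432)/39) = 0.1074.
- Power = Phi((0.273 - 1.96 x 0.1118)/0.1074) = Phi(0.50) = 69%.
- For m = -1 the same formula gives 70%.

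**4. Power with baseline TMC added.** Simulation with a Wald test of one dose against placebo: 4,000 trials per cell for m = 0 and m = -1, and 2,500 for m = -1.5. The baseline-change correlation (absolute value) is assumed. Entries are treatment-only -> adjusted power, in %.

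| Correlation | m = 0 | m = -1 | m = -1.5 |
|---|---|---|---|
| 0 | 70.4 -> 70.1 | 72.5 -> 71.6 | not run |
| 0.2 | 70.0 -> 70.1 | 68.9 -> 69.2 | no material change |
| 0.3 | 69.8 -> 71.7 | 70.5 -> 72.1 | 70 -> 71 |
| 0.4 | 70.2 -> 73.7 | 70.5 -> 74.2 | 71 -> 74 |
| 0.5 | 69.4 -> 76.1 | 70.5 -> 76.3 | 70 -> 76 |

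The Monte Carlo SE of one entry is about 0.7 points (4,000 trials) or 0.9 points (2,500). At a true difference of 2.0 with m = -1.5, power goes from 52/51/52% to 54/54/59% at correlations 0.3/0.4/0.5.

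**5. Validity.** With no true effect (m = -1; correlations 0, 0.3 and 0.5), the rejection rate is 4.5-5.0% with either model. With the effect of 2.5, the mean risk difference is 0.27-0.28 with or without the covariate, and the two agree to within 0.001.

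**6. Precision.** At correlation 0.5 and m = 0, the SD of the risk difference falls from 0.1088 to 0.1002. The variance ratio is (0.1002/0.1088)^2 = 0.85.

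**7. Odds ratio.** The median treatment-only odds ratio is about 3.2. The adjusted one is 3.4-3.5, 3.7-3.8 and 4.0-4.1 at correlations 0.3, 0.4 and 0.5. This is the usual gap between a marginal and a conditional odds ratio, not a larger effect.

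**8. Is 0.3-0.5 plausible?** If baseline and endpoint have equal variance and correlate at r, baseline correlates with change at -sqrt((1 - r)/2). Assumed r of 0.8, 0.7 and 0.5 gives magnitudes of 0.32, 0.39 and 0.50. A magnitude of 0.2 needs r = 0.92. Averaging two visits at each end raises r, and the entry cut-off narrows the baseline range, so the true value could lie below 0.3.

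**9. CGI-C and PGI-C.** The documents give no response rates for either and no association with CGI-S, PGI-S or baseline TMC, so no gain can be computed.

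**The case against.** The case for leaving the models alone is substantial.

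- **No validity problem.** Under randomisation the treatment-only test holds its level, and its confidence interval already allows for chance imbalance. This stands. A reader might infer that imbalance in baseline severity biases the responder comparison. It can shift a single realised estimate but not its expectation, and step 5 shows neither inflation nor bias.
- **The wording is not exclusive.** Calling treatment the main factor leaves room for further terms. This stands: the text supports saying that no covariate is specified, not that covariates are excluded. The ambiguity is itself a reason to list the terms.
- **The consistency argument reaches only one model.** A reader might infer that the continuous models already adjust for CGI-S and PGI-S. They do not, and CGI-C and PGI-C have no own-scale baseline. Strict inconsistency therefore applies to TMC response alone. For the other two, the argument is only that a plausible severity measure is available.
- **The gain is small and assumed.** This stands at correlations of 0.3 or less, where it is about 2 points at most.
- **Baseline-adjusted inference on TMC already exists** in the primary MMRM, the ANCOVA and the percentage-change model. That limits the consequence but does not help the global ratings.
- **Adjustment has a price.** The treatment-only model gives a marginal odds ratio and a risk difference directly. This is a fair trade-off, and standardisation recovers the marginal risk difference.

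**Conclusion.** The point holds as a minor, low-cost improvement. All three binary models leave baseline covariates unspecified although suitable ones are collected before dosing. For TMC response, adding baseline TMC would raise power from about 70% by roughly 1-2, 3-4 and 5-7 points at correlations of 0.3, 0.4 and 0.5, with about no gain or loss at 0.2 or less. This rests on 39 per arm, a true effect of 2.5, SD 3.5, normally distributed change, a placebo mean change of 0 to -1.5, and correlations that the documents do not report.

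It would be tempting to carry these gains over to CGI-C because it is the key secondary endpoint. The documents do not support that: its response rates and its link to CGI-S are not given, and its Holm test starts at 0.025 rather than the 0.05 used here. For CGI-C and PGI-C the case is one of clear pre-specification and possible, unquantified precision.

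**What to change.** Amend SAP 4.7.2.1, 4.7.2.2 and 4.7.2.4 before unblinding:

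- TMC response: treatment plus baseline TMC (mean of V0 and V1), linear.
- CGI-C: treatment plus CGI-S at V1, linear.
- PGI-C: treatment plus PGI-S at V1, linear.
- Report the adjusted odds ratio, labelled as conditional on baseline. Report the marginal risk difference by standardisation: average the predicted response probabilities over all patients' baseline values under each treatment and take the difference, with a delta-method or bootstrap 95% CI.
- Keep the treatment-only model as a sensitivity analysis.

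The cost is one covariate and a sentence or two per section, plus a short extra computation for the risk difference. No new data, visits or patients are needed. The downside is that the odds ratio becomes conditional and is not directly comparable with an unadjusted one; the sensitivity analysis supplies the marginal figure.

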## 4.7.2.3 The percentage of change in TMC score

The percentage of change in TMC score is defined as:

100 \* (TMC score at Visit x – TMC score at Baseline) / TMC score at Baseline. CONFIDENTIAL

Statistical Analysis Plan	Version 1.0		Page 22 of 37
Sponsor	SOM Biotech	Protocol No	SOMCT03

"Baseline" is the average score between V0 and V1, "Visits x" are V2, V3 and the average score between V4 and V5 or V4, V5 in case of missing visit.

For the analysis of the percentage of change in TMC score, descriptive statistics and the same MMRM model, as described for the primary endpoint will be used.

This analysis will be repeated on the PP population.

## 4.7.2.4 Patient Global Impression

The PGI-Severity (PGI-S) is a 7-point Likert Scale that asks the patients to assess the severity of their choreic symptoms at baseline ranging from not present (1) to extremely severe (7).

Then, after therapy initiation, the PGI-Change (PGI-C), asks the patients to assess the overall global change in their choreic symptoms and their quality of life since the start of study drug dosing, in a 7-point Likert Scale ranging from very much worse (7) to very much improved (1).

PGI-S will be assessed at the inclusion (Visit 1 at Day 0), and PGI-C at each following visit (from V2 to V6). For the PGI-C, patients with a score of 1 (very much improved), 2 (much improved) or 3 (minimally improved) will be defined as "Improved" and patients with a score of 4 (No change), 5 (Minimally worse), 6 (Much worse) and 7 (Very much worse) will be defined as "Not improved".

PGI-S and PGI-C results will be analysed descriptively at baseline and post-baseline visit respectively.

Logistic regression models will be performed for PGI-C at V5 (end of maintenance dose) including the treatment group as the main factor in the model. Estimates along with 95% confidence intervals for the difference in response proportion and the odds ratio of response will be derived from this model. In addition, histogram will be presented.

This analysis will be repeated on the PP population.

## 4.7.2.5 Motor part of UHDRS® (Total Motor Score, Gait and Dystonia sub-scores)

The motor part of the UHDRS® is assessed at each visit from V0 to V6, including the TMC score and the following other scores:

The **Total Motor Score (TMS)** is made of all 31 items The items are rated from 0 to 4, with 0 indicating normal findings and 4 indicating severe abnormalities. The range of the Total Motor Score (TMS) is 0 to 124, with higher scores indicating more severe motor impairment. If 7 or more item scores are missing for a given assessment, the TMS will not be calculated. If 6 or fewer item scores are missing, the last non missing score for any missing item will be used in calculating the TMS.

The gait sub-score of the UHDRS questionnaire measures the severity of gait disturbances in individuals with Huntington's disease and it is made from 3 items: gait, tandem walking and retropulsion pull test. To obtain the gait sub-score all 3 items need to be

Statistical Analysis Plan	Version 1.0		Page 23 of 37
Sponsor	SOM Biotech	Protocol No	SOMCT03

summed up. The gait sub-score ranges from 0 to 12, with higher scores indicating greater impairment.

The **dystonia sub-score of the UHDRS** questionnaire is used to evaluate the severity of dystonia in individuals with Huntington's disease and it consists of four items: trunk (involuntary movements of the trunk), right upper extremity (involuntary movements of the right arm and hand), left upper extremity (involuntary movements of the left arm and hand), right lower extremities (involuntary movements of the right leg and feet), left lower extremities (involuntary movements of the left leg and feet). The severity of dystonia is rated on a scale of 0 to 4 for each item, where 0 represents no dystonia and 4 represents severe dystonia. The scores for each item are summed to obtain the dystonia sub-score, which ranges from 0 to 20.

The analysis of the Total Motor Score (TMS) endpoint, sub-scores of gait and sub-scores of dystonia will be similar to the analysis of the primary endpoint.

Descriptive statistics for each score by visit will be presented.

The analysis of those endpoints will be based on a mixed-effect linear model for repeated measures (MMRM) to compare each active treatment group to placebo. The model will include the following factors: treatment group, visit, and treatment by-visit interaction as fixed effects, and baseline TMS score/ sub-scores of gait/ sub-scores of dystonia as covariate, depending what is analysed. An un-structured (US) variance-covariance matrix will be used to model the within-patient errors. If no reliable results under the US assumption can be obtained, the Toeplitz (TP) covariance structure, followed by the autoregressive (AR1) and Compound Symmetry (CS) covariance structure will be used. The Kenward-Roger method will be used to estimate the denominator degree of freedom.

The least squares mean (LSM) estimate for each treatment group and difference in LSM estimates at end of maintenance dose between active treatments and placebo group with their 95% confidence intervals will be provided.

For TMS, this analysis will be repeated on the PP population.

## 4.7.2.6 EQ-5D-5L measuring quality of life

EQ-5D is a standardised instrument for use as a measure of health outcome. The EQ-5D measure is designed in two parts: one descriptive part (EQ-5D) containing five dimensions of health; mobility, self-care, usual activities, pain/discomfort and anxiety/depression (5 categories, each) and a visual analogue scale (EQ-5D VAS) ranging from 'Best imaginable health state'=100 to 'Worst imaginable health state'=0.

The EQ5D is rated at the inclusion (Visit 1 at Day 0) and at the end of maintenance dose (Visit 5 at end of Week 10).

The EQ5D ratings at baseline will be compared to those after the treatment by presenting descriptive statistics for the entire questionnaire and for the difference between V1 and V5 and also for the VAS.

EQ5D dimensions and VAS will be analysed using an analysis of covariance (ANCOVA) model including treatment as fixed factor and baseline score as covariate. Results for the

Statistical Analysis Plan	Version 1.0		Page 24 of 37
Sponsor	SOM Biotech	Protocol No	SOMCT03

outcome of the primary endpoint will be presented for the least square means estimates and accompanying 95% CIs.

## 4.8 Pharmacokinetics (PK)

For plasma concentration of SOM3355 and Prolactin plasma concentration measured in all patients at each visit from Visit 1 to Visit 6 (before dosing at each visit and 2 hours after dosing at Visit 2 and Visit 4), analysis will be described in a separate Statistical Analysis Plan and results will be reported in a separate report.

**PK** analysis for the PK sub-study conducted in a sub-set of 24 patients (8/per arm) with 12-hours PK samples performed at Visit 2 (H0 before dosing, H0.5, H1, H1.5, H2, H3, H5, H8, H12) analysis will be described in a separate Statistical Analysis Plan and results will be reported separately.

#### 4.9 PK-PD assessments

PK-PD analysis is described in a separate Statistical Analysis Plan and results will be reported separately.

## 4.10 Safety

The Safety Analysis Set (SAF) will be used for the analysis of safety data. SAF includes all patients who were administered at least one dose of any study drug. Patients who are randomized and assigned a treatment but withdrew prior to dosing are not included in the safety population. Patients are included in the treatment group based on the treatment actually received.

Safety endpoints include:

- Incidence, frequency, and severity of AEs in each treatment group.
- Values and change from baseline in:
  - Vital signs: blood pressure (BP) (including orthostatic measurement), and heart rate (HR), weight.
  - o ECGs parameters (separately analysed by Banook/Phinc Development)
  - o Clinical laboratory test results (chemistry, hematology)
  - Physical examination findings,
  - Concomitant medications
  - C-SSRS assessing suicidality
  - o BDI scale assessing depression and suicidality (item #9)
  - o ESS assessing sleepiness
  - o TFC of the UHDRS® assessing functioning

Statistical Analysis Plan	Version 1.0		Page 25 of 37
Sponsor	SOM Biotech	Protocol No	SOMCT03

- FA of the UHDRS® assessing disabilities
- BARS assessing akathisia
- MoCA scale to assess cognitive disturbances
- o PBA-s to assess behavioural symptoms in HD.

Tolerability and safety data will be listed by patient (CSR section 16.2) and summarized descriptively by treatment group. Also, differences to Baseline will be presented whenever appropriate.

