# 5.7. PATIENT WITHDRAWAL CRITERIA

In accordance with the Declaration of Helsinki, patients will be free to withdraw from the study at any time if they wish to do so, for any reason specified or unspecified. Such withdrawal should not affect the required and provided medical care.

In addition, the Investigator may interrupt the patient participation from the study at any time if he/she considers it necessary for any reason including:

- Pregnancy.
- Ineligibility (either arising during the study or retrospective having been overlooked at screening).
- Significant protocol deviation.
- Significant non-compliance with treatment regimen or study requirements.
- An AE which requires discontinuation of the study medication or results in inability to continue to comply with study procedures, particularly if the patient presents a **severe depression** (BDI-21 item total score ≥30), or **suicidal ideation or behavior** (BDI-21 Item #9 >0 and active suicidal ideation in C-SSRS), or **severe hypotension** (SPB/DBP <90/60 mmHg), or **orthostatic hypotension** as defined by the ESH, or **sustained un-tolerated bradycardia** (HR <50 bpm).
- Consent withdrawn.
- Lost to follow-up.
- The Investigator or Sponsor determines it is in the best interest of the subject to discontinue the patient's participation in the study.

Patients who discontinue study treatment or active participation in the study will no longer receive study treatment but will be followed for safety. When a patient withdraws from the study, the reason(s) for withdrawal shall be recorded by the Investigator on the relevant page of the eCRF. Whenever possible, all patients who discontinue study treatment or withdraw from the study prematurely will undergo all end-of-treatment assessments. Patients who fail to return for final assessments will be contacted by the site staff. Following a minimum of 2 documented unsuccessful telephone calls, a registered letter will be sent to the patient in a final attempt to ensure protocol compliance.

It is vital to obtain follow-up data on any patient withdrawn because of an AE or SAE. In every case, efforts must be made to undertake protocol-specified, safety, follow-up procedures.

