## 1.2 Secondary objective

The secondary objectives of the study are:

- To evaluate the safety and tolerability of two doses of SOM3355 (400 mg/day and 600 mg/day) compared with placebo in HD patients, with particular attention to depression and suicidality and to the cardiovascular hemodynamic parameters.
- To evaluate the efficacy of the two doses of SOM3355 (400 mg/day and 600 mg/day) compared with placebo on:
  - o the change of Clinical Global Impression (CGI-C),
  - o the change of Patient Global Impression (PGI-C),
  - o the percentage of responders based on the improvement ≥2 in TMC score,
  - o the percentage of change of TMC score.
- A pharmacokinetic (PK) sub-study in a subset of 24 patients will allow to determine the PK profile of the two doses of SOM3355 (200 mg BID and 300 mg BID) at steady state and to model PK-PD assessments of hemodynamic and cardiac parameters. Analysis of these data will be described in a separate document and the results will be also presented in a separate report.

Statistical Analysis Plan	Version 1.0		Page 7 of 37
Sponsor	SOM Biotech	Protocol No	SOMCT03

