## 4.10.2 Vital signs

The following vital signs parameters will be assessed at each of the visits (from Visit 0 to Visit 6) as per schedule of assessment (except height only at Visit 0).

- Systolic blood pressure (SBP)
- Diastolic blood pressure (DBP)
- Heart rate
- Body weight

Four sequential measures of Blood Pressure should be performed as follows: sitting position for at least 5 minutes, supine position at least 5 minutes, standing position for 1 minute and 3 minutes. Orthostatic BP is calculated as change from supine to standing position after 1 and 3 minutes.

The following summaries will be provided:

- A summary of the observed absolute values and change from baseline in each vital sign parameter by treatment group and time point separately for sitting, supine, 1 min standing and 3 min standing
- A time profiles of the mean values for each vital sign parameter by treatment group separately for sitting, supine, 1 min standing and 3 min standing with SEM

A summary of the incidence of drop in SBP of  $\geq 20$  mmHg or drop in DBP of  $\geq 10$ mm Hg will be presented, where drop in BP is calculated as orthostatic BP.

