## The Total Score shows the severity of depression as following:

0 to 9: No depression or minimal depression

10 to 18: Mild to moderate depression

19 to 29: Moderate to severe depression

30 to 63: Severe depression

BDI will be assessed at each visit from V0 to V6.

Descriptive statistics for BDI total score as well as changes to baseline and 95 % confidence intervals will be presented at each visit. In addition, time profiles of the mean values with SEM will be created.

For BDI item #9 frequency table and shift table to baseline will be presented.

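### Safety compared with placebo is a stated objective, but SAP 4.10 plans no dose-minus-placebo safety estimate and no count of patients with HR <50 bpm, BP <90/60 mmHg or BDI total ≥30

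*SAP*

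**What the plan says.** SAP 1.2 (and Protocol 3.1) makes the safety objective comparative: both doses are to be judged "compared with placebo in HD patients, with particular attention to depression and suicidality and to the cardiovascular hemodynamic parameters".

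The planned analyses are:

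- **All safety data (SAP 4.10):** "Tolerability and safety data will be listed by patient (CSR section 16.2) and summarized descriptively by treatment group", with differences from baseline where appropriate.
- **Vital signs (SAP 4.10.2):** "A summary of the observed absolute values and change from baseline in each vital sign parameter by treatment group and time point", by posture, plus mean profiles with SEM. One categorical output is planned, the incidence of a systolic drop of at least 20 mmHg or a diastolic drop of at least 10 mmHg, which "will be presented, where drop in BP is calculated as orthostatic BP".
- **Depression (SAP 4.10.8):** "Descriptive statistics for BDI total score as well as changes to baseline and 95 % confidence intervals will be presented at each visit". Item 9 gets a frequency table and a shift table. The severity bands of the total score are printed, including 30 to 63 as severe, but no table by band is planned.
- **Suicidality (SAP 4.10.7):** counts, percentages and shifts for C-SSRS ideation and behaviour.
- **ECG (SAP 4.10.3) and PK-PD (SAP 4.9):** deferred to separate plans.

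Protocol 5.7 lists conditions under which the investigator may end a patient's participation. They include a BDI total of 30 or more, blood pressure given as "SPB/DBP <90/60 mmHg", orthostatic hypotension, and sustained bradycardia that is not tolerated, with a heart rate below 50 bpm.

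**The concern.** The objective asks for a contrast with placebo, and the analysis section never estimates one. The 95% intervals planned for BDI and several other scales attach to summaries of change from baseline, so they describe each arm and not the difference between arms. For vital signs no confidence interval is planned at all.

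The SAP is also uneven. EQ-5D-5L, last in the secondary efficacy list, gets a baseline-adjusted ANCOVA with treatment as a factor (SAP 4.7.2.6). Laboratory values get high and low frequencies, shift tables and out-of-range incidence that includes unscheduled and early-termination visits (SAP 4.10.4). BDI, heart rate and blood pressure, which the objective singles out, get no model, and absolute heart rate and blood pressure get no threshold count. Yet Protocol 2.1.6.1 names bradycardia and hypotension among the most frequent events in the earlier HD trial.

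The study is meant to find the dose to take into Phase 3 (Protocol 4.3), and the earlier HD trial went only to 400 mg/day (Protocol 2.2.1). A statement that either dose does not worsen depression, or has acceptable haemodynamics, needs an estimate against placebo and a bound on it.

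By-visit means have a further limit. A patient who crosses a Protocol 5.7 value may be withdrawn, and SAP 4.1.2 assigns the end-of-study value only to the first missed visit. That patient is absent from later by-visit means. A count of any post-baseline crossing keeps the patient in.

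**Working it through.** **1. The plan's own figure.** Protocol 9.3 and SAP 1.4 assume a difference of -2.5, an SD of 3.5 and two-sided alpha of 0.025, and give 39 per arm for at least 80% power. The exact two-sample t-test gives n = 38.5, so 39, with power 0.805. The stated 43 per arm matches 39 × 1.10 = 42.9 (39 / 0.90 = 43.3 would round up to 44). This sizes the TMC endpoint only; the documents give no precision figure for any safety comparison.

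**2. Each part of the objective against its planned output.**

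| Topic | Planned by arm | Difference from placebo with interval | Count at the Protocol 5.7 value |
|---|---|---|---|
| Orthostatic BP | yes | no | yes |
| Heart rate | yes | no | no (<50 bpm) |
| Absolute BP | yes | no | no (<90/60 mmHg) |
| BDI total | yes, with 95% CI for change | no | no (≥30) |
| BDI item 9 | frequency and shift | no | yes |
| C-SSRS | counts and shifts | no | yes |

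**3. Precision of a difference in means.** Half-width = t(0.975, 2n-2) × SD × √(2/n).

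- n = 39: 1.992 × 0.2265 = 0.45 SD.
- n = 43: 1.989 × 0.2157 = 0.43 SD.

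The documents give no SD for change in BDI. Assuming 5 to 7 points, the half-width at 39 per arm is 0.451 × 5 = 2.3 to 0.451 × 7 = 3.2 points.

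**4. Precision of counts at 43 per arm.** Event numbers are illustrative, since the documents give no rates.

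- No events in an arm: two-sided 95% upper bound = 1 - 0.025^(1/43) = 8.2%.
- 4/43 on drug against 0/43 on placebo: difference 9.3 points, Newcombe 95% CI -0.6 to 21.6.
- 6/43 against 2/43: 9.3 points, CI -3.8 to 23.0.
- 9/43 against 2/43: 16.3 points, CI 1.9 to 30.9.
- Wald half-width = 1.96 × √(p1(1-p1)/43 + p2(1-p2)/43): 9.9 points for 2% against 10%, and 16.4 points for 10% against 30%.

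Two percentages printed side by side show none of this uncertainty.

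**The case against.** Descriptive safety reporting is usual at this size. No safety hypothesis is set, and the tables put placebo beside each dose, so a reader can see the difference. An unadjusted interval can even be worked out from the N, mean and SD that SAP section 4 prescribes. Bradycardia, hypotension and depression reported as adverse events appear by preferred term and arm (SAP 4.10.1), and withdrawals are tabulated with reasons (SAP 4.2). The separate ECG plan may categorise heart rate, and the table list is a separate document that can be updated without changing the SAP (Appendix 1).

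Much of this stands. It supports reporting without tests, and it means the gap lies in estimation and not in data. It does not supply the contrast that the objective names. Adverse event terms depend on investigator reporting and not on measured values. An ECG plan cannot cover cuff blood pressure or BDI. A table list is not where an estimand or a model should first appear.

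Three stronger readings are tempting, and the documents do not support them:

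- A reader might infer that none of the protocol's haemodynamic limits is counted. The orthostatic drop is.
- A reader might infer that extreme values disappear into means. Minimum and maximum are standard output and all recorded data are listed (SAP section 4). What is missing is the number of patients per arm who cross a value.
- A reader might infer that heart rate will be judged by whether within-arm confidence intervals overlap. No such intervals are planned for vital signs.

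A count of any reading below 50 bpm is also not the Protocol 5.7 condition, which requires sustained bradycardia that is not tolerated. In addition, the blood pressure value does not say whether both components must be met.

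**Conclusion.** The point holds as a gap in estimation. The objective is comparative; SAP 4.10 describes each arm and stops there. It counts orthostatic drops, BDI item 9 and C-SSRS outcomes, but not patients with measured HR <50 bpm, BP <90/60 mmHg or BDI total ≥30.

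The unreported uncertainty is material. It is about ±0.45 SD for a mean difference at 39 per arm (2.3 to 3.2 BDI points under the assumed SD of 5 to 7), and roughly ±10 to 16 percentage points for a risk difference at 43 per arm under the assumed rates. The conclusion rests on this SAP alone; the ECG and PK-PD plans and the table list were not available. It does not imply that safety hypothesis tests are needed or that any clinical limit is wrong. The change is worth making before database lock, but the primary analysis does not depend on it.

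**What to change.** **(i) Differences in means, SAP 4.10.2 and 4.10.8.** Add each dose minus placebo with a 95% CI, adjusted for baseline, for a short prespecified list: sitting and 3-minute standing SBP and DBP, heart rate, and BDI total. Use ANCOVA at V5, or an MMRM written for the safety visits. The TMC code in SAP 4.7.1 cannot be reused unchanged: its contrasts have nine coefficients (three arms by three visit levels), whereas V2 to V5 is four visits. With ANCOVA at V5, state the number contributing per arm, since withdrawn patients may have no V5 value.

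**(ii) Counts, SAP 4.10.2, 4.10.7 and 4.10.8.** Add the number and percentage of patients per arm, with risk difference and 95% CI for each dose against placebo, for any post-baseline:

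- measured HR <50 bpm;
- SBP <90 mmHg and DBP <60 mmHg, tabulated separately;
- orthostatic drop as already defined in SAP 4.10.2;
- BDI total ≥30 and BDI item 9 >0;
- C-SSRS ideation or behaviour.

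Include unscheduled and early-termination visits, as SAP 4.10.4 already does for laboratory values.

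**(iii) Labelling.** State that these are descriptive estimates without hypothesis tests or multiplicity adjustment, and that the counts tabulate measured values and neither restate nor change the withdrawal criteria in Protocol 5.7.

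**Cost.** SAP wording and a few tables from data already collected. The downside is several unadjusted intervals, some of which may exclude zero by chance; keeping the list short and labelled limits that.
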